1 INTRODUCTION

This document is a clinical investigational plan for a human research study. The study will be conducted in accordance with the ethical principles that have their origin in the Declaration of Helsinki. By participating in the study, the Investigator agrees to adhere to all stipulations of this protocol, the conditions of IRB approval, federal and local regulatory requirements, 21CFR 812, ISO-14155 and International Conference on Harmonization Good Clinical Practice guidance ICH GCP.

This protocol describes a procedure to collect a subject's position, movement and physiological data using Masimo's Centroid system. The Centroid monitoring system consists of a noninvasive, coin-battery operated, wearable sensor that can be attached to a subject's chest or back and is intended to send the subject's position, movement and activity data to the Root monitoring station via a Bluetooth link. Device and usability data from the Centroid system as well as staff notes about the subject's demographics, vital signs, health condition, and activity will be collected. Additionally, this protocol allows for the placement of Masimo's pulse oximeter system and SedLine brain function monitoring system. The SedLine system will collect EEG data in this patient population. The pulse oximeter system will collect plethysmogram data.

1.1 Background and Rationale

Masimo Corporation is the developer of noninvasive technologies for the measurement and monitoring of physiological variables, such as arterial oxygen saturation (SpO₂), total hemoglobin concentration (SpHb), carboxyhemoglobin concentration (SpCO), methemoglobin concentration (SpMet), acoustic respiration rate monitoring (RAM), and cerebral and regional oximetry (rSO₂, O₃TM). These technologies are noninvasive and have a good patient safety record.

Masimo has developed a new noninvasive sensor named Centroid as a device to aid in preventing hospital-acquired pressure injury or worsening of existing pressure injury by monitoring patient movement, position, and orientation. The sensor is also able to detect falls through the same monitoring features. This type of monitoring may be effective in reducing the debilitating conditions for patients and their extended stays in hospitals, especially in the patient population who are vulnerable to acquire pressure injuries and/or are prone to fall-related injuries.

Each year over 2.5 million individuals in the U.S. develop a pressure injury.¹ Pressure injuries are painful, debilitating and are usually avoidable. Routine repositioning relieves and redistributes pressure over bony prominences. It is a recommended procedure to help mitigate the risks for developing a pressure injury.² The Centroid device, through detection of patient position, is a modality to ensure repositioning occurs routinely.

As many as 1 million Americans fall in the hospital every year. Falls result in fractures, lacerations, bleeding and even death. Current practices to prevent falls include assessment of patient risk, scheduled rounding practices and patient specific interventions to prevent falls.³ The Centroid device is proposed to be an additional technology to assess risk for fall based on patient position and unique modality additive to these current practices.

The Centroid system consists of a wearable, battery-operated, adhesive sensor and a back-end user interface and Root monitor display at the patient bedside as well as a central location (e.g., nursing station). The sensor contains sensing elements [REDACTED] processor, and a blue-tooth communication chip (BTLE 2.4 GHz). An algorithm [REDACTED] calculates the patient's relative position and fall as parameters [REDACTED]

[REDACTED] The system can generate alarms configured for adverse events related to patient posture, pressure injury risk and fall.

In this study, subject position data and feedback about device usability will be collected. Data collection will also be conducted for Masimo's SedLine brain function monitoring system. Secondary aims are to collect data for the pulse oximeter sensor and SedLine sensor for the purpose of correlating against Centroid sensor's data and further investigation.

1.2 Investigational Devices

RAMS0006: Calibration and Usability Validation of Patient Monitoring Device for Pressure Injury Prevention and Fall Detection
Version 2.0

The Centroid device is a non-invasive body-worn investigational device that is intended to detect the positional changes and physical movements of a subject. The device mainly consists of [REDACTED] Bluetooth LE radio, and a coin-cell lithium battery. The Centroid device is a disposable sensor that is capable of adhering to a subject's skin and continuously storing and transmitting positional data wirelessly, to a host instruments/devices to analyze the subject's activities. The sensor's skin-contacting materials are biocompatible and are thermally non-conductive. The device is intended to be used in hospitals, hospital-type facilities, healthcare facilities, and home environments.

Investigational SedLine sensors and patient cables may be used in this study. The SedLine brain function module is non-invasive and uses sensors that adhere to the subject's forehead. The SedLine brain function module uses a sophisticated multivariate algorithm to assess the patient's electroencephalogram (EEG) data from all 4 channels of the SedLine EEG sensor. The SedLine V2 sensor is intended to monitor the state of the brain by real-time data acquisition and processing of EEG signals. The SedLine system includes patient cable that connects the sensor and module to the Root multi-function monitoring system, which monitors multiple physiological parameters in healthcare environments.

2 STUDY DEVICES

2.1 Description

Investigational Devices:

Centroid monitoring device

SedLine V2 sensor and V2 patient cable

FDA-cleared Devices:

SedLine brain function module

Root monitor*

Radical-7 Pulse CO-Oximeter

LNCS SpO₂ sensors

*NOTE: during the validation stage of the study, the FDA-cleared Root monitor will be updated with Centroid software. The Root monitor at this time will be considered an investigational device, although no new patient risks will be introduced by the addition of the Centroid software.

2.2 Device Accountability

2.2.1 Receipt of Study Device

Masimo may ship or hand-carry devices and sensors to the investigative sites. Upon receipt of the study device supplies, an inventory must be performed and the Equipment Shipment Check Form ([REDACTED]) and the device accountability log will be completed for each device and signed by the receiver. It is important that the designated study staff counts and verifies that the shipment contains all the items noted in the shipment inventory. Any damaged or unusable study devices in a given shipment will be documented in the study files. The investigator must notify the study sponsor of any damaged or unusable study devices that were supplied to the investigator's site.

2.2.2 Use of Study Device

Use of devices and sensors will be documented on case report forms (CRF) for each subject. Any unused devices must be returned to the Sponsor at the end of the study or before product expiration date.

2.2.3 Return or Destruction of Study Device

At the completion of the study, there will be a final reconciliation of study devices. This reconciliation will be logged on the device accountability log. Any discrepancies noted will be investigated, resolved, and documented prior to return or

RAMS0006: Calibration and Usability Validation of Patient Monitoring Device for Pressure Injury Prevention and Fall Detection

Version 2.0

destruction of unused study devices. Devices destroyed on site will only be upon written instruction from the Sponsor and will be documented in the study files.

2.2.4 Device Deficiencies

Device deficiencies are defined as the inadequacy of a medical device with respect to its identity, quality, durability, reliability, safety or performance. Record all device deficiencies on the case report form and report to the Sponsor.

2.3 Risk/Benefits

Benefits: There will be no direct benefits to the enrolled subjects. Future benefits to subjects include effective pressure injury prevention (i.e., reduction in their occurrence and/or severity) and detection of hospital falls.

Centroid device risks: As with all wearable sensors, the Centroid sensor has a risk of thermal burn as there is a coin battery in the sensor. The coin battery used in the Centroid device is widely used in other commercially available medical devices for wearable monitoring applications. Masimo's design includes safeguards against thermal burn, and this risk is believed to be low. Sensors will be attached with a medical-grade, biocompatible adhesive. Marks may appear on the skin beneath the sensor due to adhesion for a long period (from several hours to days). The risk is believed to be low. The sensor transmits that data, after on-sensor processing, via a radio link to the host device.

SEDLine V2 sensor and V2 patient cable risks: All patient-contact materials, including the adhesive used in the design of the Masimo sensors, have been subjected to biocompatibility tests per ISO 10993-1 and results demonstrate that the materials are non-toxic, non-irritating, and non-sensitizing. The sensors have been evaluated for mechanical and electrical safety and the risks have been determined to be minimal. The modifications to the sensor are specifically designed so as not to introduce any new risks to the subject.

Pulse oximeter risks: The Radical-7 pulse CO-oximeter device and LNCS® pulse oximeter sensors used in this study are FDA-cleared.

Root patient monitoring system risks: The Masimo Root Monitoring System and SedLine brain function module used during this study are FDA-cleared devices.

3 STUDY OBJECTIVES

The primary aim of this study is to collect data for *calibration* and *usability validation* of the new Centroid monitoring system which Masimo has developed for monitoring a patient's position and movement to prevent pressure injury and detecting falls in the hospital. This protocol describes data collection from patient volunteers during their routine hospital stay lasting usually for more than one day. During the calibration phase, positional data will be collected for the purpose of evaluating the Centroid design and technology.

Secondary aims are to collect data for the pulse oximeter sensor and SedLine sensor for the purpose of correlating against Centroid sensor's data and further investigation.

4 STUDY DESIGN

4.1 General Design

This is a prospective clinical study of Masimo's Centroid sensor in patients to collect movement, position, and other physiological data from a sensor placed on the subject's chest or back. LNCS pulse oximeter sensors will be placed on subjects according to their tolerance of the sensors. SedLine sensors may be placed on subjects while they are asleep.

4.2 Study Endpoint

RAMS0006: Calibration and Usability Validation of Patient Monitoring Device for Pressure Injury Prevention and Fall Detection
Version 2.0

For the data collection and calibration phase of the study, there are no study endpoints. For the centroid usability validation phase of the study, user feedback will be collected from a questionnaire and analyzed

[REDACTED]

[REDACTED]

6 SUBJECT SELECTION AND WITHDRAWAL

6.1 Population Base

Subjects will be at least 18 years of age. Subjects will be recruited from Baylor University Medical Center. A total enrollment of at least 60 unique subjects is targeted.

6.2 Inclusion Criteria

- At least 18 years of age
- ICU patient
- Primarily bedbound subjects
- Able to be monitored for a minimum of approximately 8 hours

6.3 Exclusion Criteria

- Pregnancy
- Prisoner status
- Pressure injury stage 2, 3, or ungroupable
- Has a pacemaker or internal defibrillator
- Has a history of complications with a similar study
- Has any medical condition which in the judgment of the Investigator, renders them inappropriate for participation in this study

6.4 Study Timelines

Each individual subject may participate in this study from approximately 8 hours to 16 hours. Data collection may start only after the informed consent has been signed by the participant. The subject will be considered to have completed the study after at least 8 hours of Centroid data have been collected. The study is expected to be completed within 12 months of initiation.

6.5 Subject Recruitment and Screening

Following identification of a potential subject, the patient will be approached by the principal investigator or a designated research staff member, who will explain the purpose and procedures of the study. If the patient expresses interest in participating in the study, they will be asked to read the written Informed Consent Form in English or Spanish depending on the patient's language preference.

All items of the Informed Consent will be explained in a way that is easily understandable, for either English or Spanish speaking subjects. The patient will be given adequate time to read through the Informed Consent, and they will be given adequate time and privacy to consider the decision of whether or not to sign the Informed Consent Form. Once all of the patient's questions have been answered and the Informed Consent Form signed, the patient is now adequately consented.

RAMS0006: Calibration and Usability Validation of Patient Monitoring Device for Pressure Injury Prevention and Fall Detection
Version 2.0

Now the patient will be enrolled as a study subject, at which time the subject will be assigned a study identification number or enrollment number.

All subjects will have their medical history reviewed at the time of screening by either the PI or the study staff who is delegated for this task. Subjects will be evaluated based on the inclusion and exclusion criteria to determine eligibility to be enrolled into the study. If a subject is deemed ineligible after screening, the subject will be withdrawn from the study.

Information regarding the subject's demographic (including, but not limited to age, weight, race, ethnicity, etc.), preexisting allergies, skin abnormalities, and other preexisting diseases/conditions that may be relevant to the study will be recorded within a paper-based Case Report Form (CRF).

HIPAA

The pre-screening of patients will require the investigators to access personal health information to identify prospective subjects without HIPAA authorization prior to obtaining written informed consent for the study. Informed consent and HIPAA authorization will be obtained during recruitment and screening procedures as described in previous sections of this clinical investigation plan; however, pre-screening process would require a waiver of HIPAA authorization, as the research study could not be practicably carried out without this implied waiver of consent. The participants' rights and welfare will not be adversely affected by waiving consent. Patients' protected health information (PHI) will not be inappropriately reused or disclosed to any other person or entity. To further safeguard all protected health information, the data collected during the study will not be labeled with any personal identifying information, or with a code that this research team can link to personal identifying information. The data will not be stored with any protected health information identifiers.

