6.6 Early Withdrawal of Subjects

6.6.1 Withdrawal of Individual Subjects

Subjects can leave the study at any time for any reason if they wish to do so without any consequences or loss of benefits to which they are otherwise entitled. Subjects may be withdrawn from the study prior to expected completion for reasons such as safety concerns, failure to adhere to protocol requirements, subject consent withdrawal, etc.

Any data collected until the time of subject withdrawal may be included in the final data analysis. Information on the subject's withdrawal should be documented in the case report form and should include clear documentation of the reason for withdrawal to the Sponsor.

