6.6.3 Replacement of individual subjects after withdrawal

In case a subject leaves the study prematurely, another volunteer may be recruited.

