8 SAMPLE SIZE AND STATISTICAL CONSIDERATIONS

8.1 Calibration and Validation stage

The calibration stage will continue until a sufficient number of cases have been obtained with quality data (e.g. no data drop-outs). Initial data sets may be considered training sets and may not be used for device calibration. Documentation will be included in the study records of when the calibration stage has concluded and when the validation stage commenced.

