8.2 Usability validation

In the validation stage, since this is a usability validation only, there is no statistical justification needed for the sample size. The study will enroll at least 30 subjects for this stage.

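### Does Section 6.5's unclear point of enrolment undermine the targets of at least 60 and at least 30 subjects?

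*Combined protocol and SAP*

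**What the plan says.** Three sentences of Section 6.5 bear on when a patient becomes enrolled. In the order in which they appear:

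1. After the consent form is signed: "Now the patient will be enrolled as a study subject, at which time the subject will be assigned a study identification number".
2. After the medical history review: "Subjects will be evaluated based on the inclusion and exclusion criteria to determine eligibility to be enrolled into the study".
3. Immediately afterwards: "If a subject is deemed ineligible after screening, the subject will be withdrawn from the study".

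The numerical targets are stated in terms of enrolment. Section 6.1 says "A total enrollment of at least 60 unique subjects is targeted", and Section 8.2 says of the validation stage "The study will enroll at least 30 subjects for this stage". Section 8.1 gives calibration no number of its own: "The calibration stage will continue until a sufficient number of cases have been obtained with quality data". If a subject leaves early, Section 6.6.3 says "another volunteer may be recruited". Section 6.6.1 requires withdrawals to be documented in the case report form, and that record "should include clear documentation of the reason for withdrawal to the Sponsor".

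**The concern.** A patient who is already enrolled and numbered cannot still be under assessment for eligibility to enrol. Taken literally, the text of 6.5 supports two definitions:

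- **Reading A:** enrolment happens at consent. A patient then found ineligible is an enrolled subject who was withdrawn.
- **Reading B:** enrolment follows the eligibility check. That patient was never enrolled.

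Both targets count enrolled subjects, so two people following 6.5 could reach 30 or 60 at different points. They could also report different numbers of withdrawals, because reading A puts patients found ineligible in the same category as those who left after wearing the sensor. Replacement is optional, so it does not force the two counts together. If the targets carried a precision or power claim, the difference could leave the study short of the information it was meant to have.

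**Working it through.** **Which reading the text supports.** Section 6.5 describes a sequence: consent, enrolment and numbering, history review, withdrawal if ineligible. Sentences 1 and 3 both fit reading A. Only the closing phrase of sentence 2 points to reading B; without it, the paragraph is consistent. Other sections are compatible with A. Section 11.3 lists the inclusion and exclusion criteria among the contents of the form completed for enrolled subjects. Section 14 requires consent before enrolment and is silent on eligibility.

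**Reproducing the plan's figures.** There is nothing to reproduce. The targets of 60 and 30 come with no error rate, power, effect size or dropout rate, and Section 8.2 says that no statistical justification is needed.

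**Size of the gap.** Let *N* be the target and *s* the share found ineligible after consent. The documents do not give *s*; the values below are assumptions.

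- Reading A: eligible subjects left = *N*(1 − *s*)
- Reading B: consents needed = *N*/(1 − *s*), rounded up

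| Assumed *s* | A: eligible from 30 | A: eligible from 60 | B: consents for 30 | B: consents for 60 |
|---|---|---|---|---|
| 0% | 30 | 60 | 30 | 60 |
| 5% | 28.5 | 57 | 32 | 64 |
| 10% | 27 | 54 | 34 | 67 |
| 20% | 24 | 48 | 38 | 75 |
| 30% | 21 | 42 | 43 | 86 |

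For example, at 10%: 30 × 0.9 = 27, and 30/0.9 = 33.3, rounded up to 34. The readings agree if nobody is found ineligible after consent. Subjects who pass screening and leave early are enrolled under both readings, so they must be kept out of *s*. Section 6.5 also allows records to be reviewed before consent to identify prospective subjects, which should keep *s* towards the top of the table.

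**Withdrawal proportion.** Suppose 3 of 30 consented patients are ineligible and 2 of the remaining 27 leave early (both assumed). Reading A gives (3 + 2)/30 = 16.7% withdrawn; reading B gives 2/27 = 7.4%. The ratio looks large, but the visible plan does not name a withdrawal proportion as an outcome. The reason recorded under 6.6.1 lets an analyst separate the 3 from the 2.

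**What depends on the count.** Section 4.2 gives calibration no endpoints, and 8.1 ends that stage on data quality rather than on a number. Validation is an analysis of questionnaire feedback, with no visible hypothesis test or precision target. Both 30 and 60 are minimums, so enrolling a few more patients is already within the plan.

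**The case for a change.** The best argument for a change is that the contradiction stands in current text, that enrolment is the unit of the only two numerical targets, and that no visible section says whether subjects withdrawn as ineligible count. Completion is defined in Section 6.4 as at least 8 hours of Centroid data, but neither target refers to completers. Section 6.6.1 allows data collected up to withdrawal to be used, so under reading A it could cover data from a patient later found ineligible. The visible text makes consent, not a confirmed eligibility decision, the condition for starting data collection. The remedy would cost only a few words.

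The wording point stands: 6.5 is internally inconsistent, and defining enrolment once would be tidier. The consequences are weaker.

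- The 6.4 completion rule already lets an analyst report completers separately from those merely enrolled.
- The use of data up to withdrawal is permitted, not required, and the recorded reason identifies ineligible patients.
- The monitor's check of adherence to the criteria (12.5) is needed under either reading, because a patient can be enrolled in error under both.
- Whether validation needs its own data-quality rule, and who gives feedback after early sensor removal, are separate questions that do not arise from the enrolment wording. The feedback question also touches redacted text in 4.2.

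One section was removed before review and others are partly redacted, so a definition of which subjects count may exist there. It would not cure the wording of 6.5, but it could settle the targets.

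**Conclusion.** The inconsistency in 6.5 is genuine but clerical, and no change to the plan follows. One phrase departs from a sequence that otherwise puts enrolment at consent. The two readings differ only by the patients found ineligible after consent: at an assumed 10%, 3 fewer eligible subjects out of 30, or 4 extra consents to reach 30 eligible; at an assumed 20%, 6 fewer or 8 extra. These rates are illustrations; if pre-screening works well the difference may be close to zero.

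The conclusion rests on the visible text: minimum targets with no statistical calculation behind them, no calibration endpoint, questionnaire feedback as the validation output, optional replacement, and a recorded reason for each withdrawal. On that basis an analyst can report consented, eligible, withdrawn and completed subjects separately, and no planned result depends on which of them is called enrolled. The conclusion would differ if the redacted part of 4.2 set an acceptance criterion that depends on the number enrolled; nothing visible suggests one.
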